2.2.1.2 When the patient has only non-measurable disease

This circumstance arises in some trials when it is not a criterion of study entry to have measurable disease. The same general concepts apply here as noted above, however, in this instance there is no measurable disease assessment to factor into the interpretation of an increase in non-measurable disease burden. Because worsening in non-target disease cannot be easily quantified (by definition: if all lesions are truly non-measurable) a useful test that can be applied when assessing patients for

unequivocal progression is to consider if the increase in overall disease burden based on the change in non-measurable disease is comparable in magnitude to the increase that would be required to declare PD for measurable disease: ie, an increase in tumor burden representing an additional 73% increase in ‘volume’ (which is equivalent to a 20% increase diameter in a measurable lesion). Examples include, an increase in lymphangitic disease from localized to widespread, or may be described as ‘sufficient to require a change in therapy’. If ‘unequivocal progression’ is seen, the patient should be considered to have had overall PD at that point. While it would be ideal to have objective criteria to apply to non-measurable disease, the very nature of that disease makes it impossible to do so; therefore the increase must be substantial.

2.2.2 New Lesions

The appearance of new malignant lesions denotes disease progression; therefore, some comments on detection of new lesions are important. There are no specific criteria for the identification of new radiographic lesions; however, the finding of a new lesion should be unequivocal: ie, not attributable to differences in scanning technique, change in imaging modality or findings thought to represent something other than tumor (for example, some ‘new’ bone lesions may be simply healing or flare of pre-existing lesions). This is particularly important when the patient’s baseline lesions show partial or complete response. For example, necrosis of a liver lesion may be reported on a CT scan report as a ‘new’ cystic lesion, which it is not.

NOTE: Fluid collections (pleural effusions, pericardial effusions, and ascites) will not be considered new lesions and will not contribute to response or progression. In the event a new fluid collection is seen on a post-baseline imaging exam, a comment may be made, but the appearance of a new fluid collection alone should not result in an assessment of Progressive Disease (PD). A lesion identified on a follow-up study in an anatomical location that was not scanned at baseline is considered a new lesion and will indicate disease progression. An example of this is the patient who has visceral disease at baseline and while on study has a CT or MRI brain ordered which reveals metastases. The patient’s brain metastases are considered to be evidence of PD even if he/she did not have brain imaging at baseline. A lesion identified on Chest X-Ray that was not present in prior CT can be considered a new lesion and will result in Progressive Disease (PD).

If a new lesion is equivocal, for example because of its small size, continued follow-up evaluation will clarify if it represents truly new disease. If repeat scans confirm there is definitely a new lesion, then progression should be declared using the date of the initial scan. While FDG-PET response assessments need additional study, it is sometimes reasonable to incorporate the use of FDG-PET scanning to complement CT scanning in assessment of progression (particularly possible ‘new’ disease). New lesions on the basis of FDG-PET imaging can be identified according to the following algorithm:

1. Negative FDG-PET at baseline, with a positive FDG-PET at follow-up is a sign of PD based on a new lesion.
2. No FDG-PET at baseline and a positive FDG-PET at follow-up: If the positive FDG-PET at follow-up corresponds to a new site of disease confirmed by CT, this is PD. If the positive FDG-PET at follow-up is not confirmed as a new site of disease on CT, additional follow-up CT scans are needed to determine if there is truly progression occurring at that site (if so, the

date of PD will be the date of the initial abnormal FDG-PET scan). If the positive FDG-PET at follow-up corresponds to a pre-existing site of disease on CT that is not progressing on the basis of the anatomic images, this is not PD.

2.3 Response Assessment

2.3.1 Evaluation of Best Overall Response

The best overall response is the best response recorded from the start of the study treatment until disease progression or the last response recorded, taking into account any requirement for confirmation and censoring rules regarding subsequent therapy. The patient’s best overall response assignment will depend on the findings of both target and non-target disease and will also take into consideration the appearance of new lesions. Furthermore, depending on the nature of the study and the protocol requirements, it may also require confirmatory measurement.

2.3.2 Time Point Response

At each protocol specified time point, a response assessment occurs. Table 2.3.2-1 provides a summary of the overall response status calculation at each time point for patients who have measurable disease at baseline. When patients have non-measurable (therefore non-target) disease only, Table 2.3.2-2 is to be used.

Target Lesions	Non-Target Lesions	New Lesions	Overall Response
CR	CR	No	CR
CR	Non-CR/non-PD	No	PR
CR	Not evaluated	No	PR
PR	Non-PD or not all evaluated	No	PR
SD	Non-PD or not all evaluated	No	SD
Not all evaluated	Non-PD	No	NE
PD	Any	Yes or No	PD
Any	PD	Yes or No	PD
Any	Any	Yes	PD

CR, complete response; PR, partial response, SD, stable disease; PD, progressive disease; N, inevaluable.

Non-Target Lesions	New Lesions	Overall Response
CR	No	CR
Non-CR/non-PD	No	Non-CR/non-PD ^a

Table 2.3.2-2: Time Point Response: Patients with Non-target Disease Only		
Non-Target Lesions	New Lesions	Overall Response
Not all evaluated	No	NE
Unequivocal PD	Yes or No	PD
Any	Yes	PD

CR, complete response; PD, progressive disease; NE, inevaluable.

^a Non-CR/non-PD is preferred over SD for non-target disease since SD is increasingly used as endpoint for assessment of efficacy in some trials so to assign this category when no lesions can be measured is not advised.

2.3.3 Best Overall Response

Best response determination of complete or partial response requires confirmation: Complete or partial responses may be claimed only if the criteria for each are met at a subsequent time point of ≥ 4 weeks (28 days) later. In this circumstance, the best overall response can be interpreted as in Table 2.3.3-1. When SD is believed to be best response, it must meet the protocol specified minimum time from the date of first treatment or randomization date.

For example, if the first scheduled follow-up imaging visit is Week 6 (± 7 days) for a particular protocol, a Best Response of SD can only be made after the subject is on-study for a minimum of 6 weeks (42 days) minus 7 days, for an absolute minimum time on-study of 35 days from the reference start date (reference date is considered Day 1 on study). If the subject is not on-study for at least this amount of time, any tumor assessment indicating stable disease before this time period will have a Best Response of NE unless PD is identified.

Special note on response assessment: When nodal disease is included in the sum of target lesions and the nodes decrease to ‘normal’ size (< 10 mm), they may still have a measurement reported on scans. This measurement should be recorded even though the nodes are normal in order not to overstate progression should it be based on increase in size of the nodes. As noted earlier, this means that patients with CR may not have a total sum of ‘zero’ on the case report form (CRF).

Table 2.3.3-1: Best Overall Response (Confirmation of CR and PR Required)		
Overall Response First Time Point	Overall Response Subsequent Time Point	Best Overall Response
CR	CR	CR
CR	PR	SD, PD OR PR ^a
CR	SD	SD provided minimum criteria for SD duration met, otherwise, PD
CR	PD	SD provided minimum criteria for SD duration met, otherwise, PD
CR	NE	SD provided minimum criteria for SD duration met, otherwise, NE
PR	CR	PR

Table 2.3.3-1: Best Overall Response (Confirmation of CR and PR Required)		
Overall Response First Time Point	Overall Response Subsequent Time Point	Best Overall Response
PR	PR	PR
PR	SD	SD
PR	PD	SD provided minimum criteria for SD duration met, otherwise, PD
PR	NE	SD provided minimum criteria for SD duration met, otherwise, NE
NE	NE	NE

CR, complete response; PR, partial response; SD, stable disease; PD, progressive disease; NE, inevaluable.

^a If a CR is truly met at first time point, then any disease seen at a subsequent time point, even disease meeting PR criteria relative to baseline, makes the disease PD at that point (since disease must have reappeared after CR). Best response would depend on whether minimum duration for SD was met. However, sometimes ‘CR’ may be claimed when subsequent scans suggest small lesions were likely still present and in fact the patient had PR, not CR at the first time point. Under these circumstances, the original CR should be changed to PR and the best response is PR.

2.3.4 Confirmation Scans

Verification of Response: To be assigned a status of CR or PR, changes in tumor measurements must be confirmed by consecutive or subsequent repeat assessments that should be performed no less than 28 days after the criteria for response are first met. Subsequent documentation of a CR may provide confirmation of a previously identified CR even with an intervening NE or PR (eg, CR NE CR or CR PR CR). Subsequent documentation of a PR may provide confirmation of a previously identified PR even with an intervening NE or SD (eg, PR NE PR or PR SD PR). However, only one (1) intervening time point will be allowed between PR/CRs for confirmation.

Verification of Progression: Progression of disease should be verified in cases where progression is equivocal. If repeat scans confirm PD, then progression should be declared using the date of the initial scan. If repeat scans do not confirm PD, then the subject is considered to not have progressive disease.

REFERENCES

¹ Eisenhauer EA, Therasse P, Bogaerts J, et al. New response evaluation criteria in solid tumors: revised RECIST guideline (version 1.1). Eur J Cancer 2009; 45: 228-47.

APPENDIX 6 MANAGEMENT ALGORITHMS

These general guidelines constitute guidance to the Investigator and may be supplemented by discussions with the Medical Monitor representing the Sponsor. The guidance applies to all immuno-oncology agents and regimens.

A general principle is that differential diagnoses should be diligently evaluated according to standard medical practice. Non-inflammatory etiologies should be considered and appropriately treated.

Corticosteroids are a primary therapy for immuno-oncology drug-related adverse events. The oral equivalent of the recommended IV doses may be considered for ambulatory patients with low-grade toxicity. The lower bioavailability of oral corticosteroids should be taken into account when switching to the equivalent dose of oral corticosteroids.

[figure not shown]
Consultation with a medical or surgical specialist, especially prior to an invasive diagnostic or therapeutic procedure, is recommended.

The frequency and severity of the related adverse events covered by these algorithms will depend on the immuno-oncology agent or regimen being used.

All AEs/SAEs toxicity management are to be managed using CTCAE v5.

GI Adverse Event Management Algorithm

Rule out non-inflammatory causes. If non-inflammatory cause is identified, treat accordingly and continue I-O therapy.
Opiates/narcotics may mask symptoms of perforation. Infliximab should not be used in cases of perforation or sepsis.

[figure not shown]
Patients on IV steroids may be switched to an equivalent dose of oral corticosteroids (eg, prednisone) at start of tapering or earlier, after sustained clinical improvement is observed. Lower bioavailability of oral corticosteroids should be taken into account when switching to the equivalent dose of oral corticosteroids.

* Discontinue for Grade 4 diarrhea or colitis. For Grade 3 diarrhea or colitis, 1) Nivolumab monotherapy: Nivolumab can be delayed. 2) Nivolumab+ Ipilimumab combination: Ipilimumab should be discontinued while nivolumab can be delayed. Nivolumab monotherapy can be resumed when symptoms improve to Grade 1. Please refer to protocol for dose delay and discontinue criteria for other combinations.

28-Sep-2020

Renal Adverse Event Management Algorithm

Rule out non-inflammatory causes. If non-inflammatory cause, treat accordingly and continue I-O therapy.

[figure not shown]

Patients on IV steroids may be switched to an equivalent dose of oral corticosteroids (eg, prednisone) at start of tapering or earlier, after sustained clinical improvement is observed. Lower bioavailability of oral corticosteroids should be taken into account when switching to the equivalent dose of oral corticosteroids.

28-Sep-2020

Pulmonary Adverse Event Management Algorithm

Rule out non-inflammatory causes. If non-inflammatory cause, treat accordingly and continue I-O therapy.
Evaluate with imaging and pulmonary consultation.

[figure not shown]

Patients on IV steroids may be switched to an equivalent dose of oral corticosteroids (eg, prednisone) at start of tapering or earlier, after sustained clinical improvement is observed. Lower bioavailability of oral corticosteroids should be taken into account when switching to the equivalent dose of oral corticosteroids.

28-Sep-2020

Hepatic Adverse Event Management Algorithm

Rule out non-inflammatory causes. If non-inflammatory cause, treat accordingly and continue I-O therapy.
Consider imaging for obstruction.

Patients on IV steroids may be switched to an equivalent dose of oral corticosteroids (e.g. prednisone) at start of tapering or earlier, after sustained clinical improvement is observed. Lower bioavailability of oral corticosteroids should be taken into account when switching to the equivalent dose of oral corticosteroids.

[figure not shown]
^Λ Please refer to protocol dose delay and discontinue criteria for specific details.

*The recommended starting dose for AST or ALT > 20 x ULN or bilirubin >10 x ULN is 2 mg/kg/day methylprednisolone IV.

28-Sep-2020

Endocrinopathy Adverse Event Management Algorithm

Rule out non-inflammatory causes. If non-inflammatory cause, treat accordingly and continue I-O therapy.
Consider visual field testing, endocrinology consultation, and imaging.

[figure not shown]

Patients on IV steroids may be switched to an equivalent dose of oral corticosteroids (eg, prednisone) at start of tapering or earlier, after sustained clinical improvement is observed. Lower bioavailability of oral corticosteroids should be taken into account when switching to the equivalent dose of oral corticosteroids.

28-Sep-2020

Skin Adverse Event Management Algorithm

Rule out non-inflammatory causes. If non-inflammatory cause, treat accordingly and continue I-O therapy.

Patients on IV steroids may be switched to an equivalent dose of oral corticosteroids (e.g. prednisone) at start of tapering or earlier, after sustained clinical improvement is observed. Lower bioavailability of oral corticosteroids should be taken into account when switching to the equivalent dose of oral corticosteroids.

[figure not shown]
*Refer to NCI CTCAE v5 for term-specific grading criteria.

^If Steven-Johnson Syndrome (SJS), toxic epidermal necrosis (TEN), Drug Reaction with Eosinophilia and Systemic Symptoms (DRESS) is suspected, withhold I-O therapy and refer patient for specialized care for assessment and treatment. If SJS, TEN, or DRESS is diagnosed, permanently discontinue I-O therapy.

28-Sep-2020

Neurological Adverse Event Management Algorithm

Rule out non-inflammatory causes. If non-inflammatory cause, treat accordingly and continue I-O therapy.

[figure not shown]
Patients on IV steroids may be switched to an equivalent dose of oral corticosteroids (eg. prednisone) at start of tapering or earlier, after sustained clinical improvement is observed. Lower bioavailability of oral corticosteroids should be taken into account when switching to the equivalent dose of oral corticosteroids.

[^]Discontinue for any grade myasthenia gravis, Guillain-Barre syndrome, treatment-related myelitis, or encephalitis.

28-Sep-2020

Myocarditis Adverse Event Management Algorithm

Rule out non-inflammatory causes. If non-inflammatory cause, treat accordingly and continue I-O therapy.

Patients on IV steroids may be switched to an equivalent dose of oral corticosteroids (eg, prednisone) at start of tapering or earlier, after sustained clinical improvement is observed. Lower bioavailability of oral corticosteroids should be taken into account when switching to the equivalent dose of oral corticosteroids. Prophylactic antibiotics should be considered in the setting of ongoing immunosuppression.

28-Sep-2020

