7.4.1 Dose Delay Criteria for Nivolumab, Ipilimumab, and BMS-986207

The criteria for dose delay, resumption, and discontinuation in [Table 7.4.2-1](#) applies to ipilimumab, nivolumab, and BMS-986207 or its placebo. Since this study is single-blinded, the criteria in [Table 7.4.2-1](#) for BMS-986207 or its placebo will be the same as that for nivolumab.

Dose delay criteria apply for all drug-related AEs, regardless of whether the event is attributed to BMS-986207, nivolumab or ipilimumab. Delay administration of all study interventions (BMS-986207, nivolumab, and ipilimumab) if any of the delay criteria in [Table 7.4.2-1](#) are met. Delay all study medication dosing for any AE, laboratory abnormality, or intercurrent illness which, in the judgment of the investigator, warrants delaying the dose of study medication.

For participants who require delay of study interventions, re-evaluate weekly, or more frequently, if clinically indicated and resume dosing when criteria to resume treatment are met (see [Section](#)

7.4.2). Continue tumor assessments per protocol even if dosing is delayed. See [Section 8.1](#) for further information regarding permanent discontinuation of study interventions.

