7.4.2 Criteria to Resume Treatment

Participants may resume treatment with study intervention if they have completed AE management (ie, corticosteroid taper) or are on ≤ 10 mg prednisone or equivalent, and meet the requirements per [Table 7.4.2-1](#).

Prior to re-initiating treatment in a participant with a dosing delay lasting > 8 weeks, the Sponsor/Medical Monitor (or designee) must be consulted and treatment decision agreed upon. Continue tumor assessments per protocol even if dosing is delayed. Continue periodic study visits to assess safety and laboratory studies every 3 weeks or more frequently if clinically indicated during such dosing delays.

When criteria to resume treatment are met, resume all study interventions (BMS-986207 or its placebo, nivolumab and ipilimumab) on the same day unless the investigator determines that one of the agents must be discontinued due to toxicity attributed to that agent alone. Since this study is blinded, criteria for dose delay, resumption, and discontinuation in [Table 7.4.2-1](#) for BMS-986207 or its placebo will be the same as that for nivolumab. Thus, if nivolumab is resumed, BMS-986207 or its placebo will also resume. Treatment with BMS-986207 or its placebo will not resume without nivolumab.

Dose delay is required for participants with confirmed SARS-CoV-2 infection. Participants with confirmed SARS-CoV-2 infection may resume treatment after 1) at least 10 days (20 days for severe/critical illness) have passed since symptoms first appeared, positive RT-PCR test result, or positive viral antigen test result, 2) resolution of acute symptoms (including at least 24 hours has passed since last fever without fever reducing medications), 3) evaluation by the Investigator with confirmation that there are no sequelae that would place the participant at a higher risk of receiving investigational treatment, and 4) consultation by the Sponsor/Medical Monitor (or designee). For suspected cases, treatment may also resume if SARS-CoV-2 infection is ruled-out and other criteria to resume treatment are met.

Prior to re-initiating on-study intervention in a participant with a dosing delay lasting > 8 weeks due to SARS-CoV-2 infection, the Sponsor/Medical Monitor (or designee) must be consulted.

Table 7.4.2-1: Adverse Event Criteria for Delay, Resume, and Discontinue of Nivolumab, Ipilimumab, and BMS-986207

Drug-Related AE per CTCAE V5	Severity	Action Taken	Clarifications, Exceptions, and Resume Criteria

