Gastrointestinal			
Colitis or Diarrhea	Grade 2	Delay dose	Dosing may resume when AE resolves to baseline
	Grade 3	Permanently discontinue Ipilimumab	Nivolumab + BMS-986207 may be resumed when AE resolves to baseline. If Grade 3 diarrhea or colitis recurs while on nivolumab + BMS-986207, permanently discontinue
	Grade 4	Permanently discontinue	
Renal			
Serum Creatinine Increased	Grade 2 or 3	Delay dose	Dosing may resume when AE resolves to Grade ≤ 1 or baseline value
	Grade 4	Permanently discontinue	
Pulmonary			
Pneumonitis	Grade 2	Delay dose	Dosing may resume after pneumonitis has resolved to \leq Grade 1.
	Grade 3 or 4	Permanently discontinue	
Hepatic			
AST, ALT, or T.bili increased	AST or ALT $> 3x$ and $\leq 5x$ ULN or T.Bili $> 1.5x$ and $\leq 3x$ ULN, regardless of baseline value	Delay dose or permanently discontinue	If the abnormality is not associated with new signs/symptoms of liver inflammation, dosing may resume when laboratory values return to baseline. If AST or ALT elevation and symptomatic liver inflammation (eg, right upper quadrant tenderness, jaundice), then permanently discontinue.
	AST or ALT $> 5x$ ULN or T.bili $> 3x$ ULN, regardless of baseline value	Delay dose or permanently discontinue	In most cases of AST or ALT $> 5x$ ULN, study intervention will be permanently discontinued. If the investigator determines a possible favorable benefit/risk ratio that warrants continuation of study intervention, a discussion between the

Table 7.4.2-1: Adverse Event Criteria for Delay, Resume, and Discontinue of Nivolumab, Ipilimumab, and BMS-986207

Drug-Related AE per CTCAE V5	Severity	Action Taken	Clarifications, Exceptions, and Resume Criteria
			investigator and the Sponsor/Medical Monitor (or designee) must occur and approval from Sponsor/Medical Monitor (or designee) prior to resuming therapy.
	Concurrent AST or ALT > 3 x ULN and T.bili > 2 x ULN, regardless of baseline value	Permanently discontinue	
Endocrinopathy			
Adrenal Insufficiency	Grade 2 adrenal insufficiency	Delay dose	Dosing may resume after adequately controlled with hormone replacement.
	Grade 3 or 4 adrenal insufficiency or adrenal crisis	Delay dose or permanently discontinue	Mandatory discussion with and approval from the Sponsor/Medical Monitor (or designee) needed prior to resuming therapy. If adrenal insufficiency resolves or is adequately controlled with physiologic hormone replacement, participant may not require discontinuation of study drug.

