7.4.3 Management Algorithms for Nivolumab plus Ipilimumab ± BMS-986207

IO agents are associated with AEs that can differ in severity and duration from AEs caused by other therapeutic classes. Nivolumab, ipilimumab, and BMS-986207 are considered IO agents and the management algorithms in [Appendix 6](#) provide guidance on assessing and managing the following groups of AEs:

- Gastrointestinal
- Renal
- Pulmonary
- Hepatic
- Endocrinopathy
- Skin
- Neurological
- Myocarditis

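### After Grade 3 diarrhea or colitis, the Appendix 6 GI footnote and Table 7.4.2-1 set different recovery thresholds for resuming nivolumab, and no sentence says which prevails

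*Combined protocol and SAP*

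**What the plan says.** Two places give a condition for restarting treatment after Grade 3 diarrhea or colitis.

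- **Appendix 6, GI algorithm footnote.** For the nivolumab plus ipilimumab combination, ipilimumab is to be stopped and nivolumab may be delayed. Then: "Nivolumab monotherapy can be resumed when symptoms improve to Grade 1". The footnote closes: "Please refer to protocol for dose delay and discontinue criteria for other combinations".
- **Table 7.4.2-1 (Section 7.4.2), Grade 3 row for colitis or diarrhea.** Ipilimumab is permanently discontinued. Then: "Nivolumab + BMS-986207 may be resumed when AE resolves to baseline". If the Grade 3 event recurs after that, treatment is permanently discontinued.

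The surrounding text bears on which passage a site would use.

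- Section 7.4.1 says that the table's delay, resumption and discontinuation criteria cover every study drug; the table "applies to ipilimumab, nivolumab, and BMS-986207 or its placebo".
- Section 7.4.2 makes resumption conditional on the table's requirements. It ties the blinded product to nivolumab: "Thus, if nivolumab is resumed, BMS-986207 or its placebo will also resume".
- Section 8.1.1 says that if only ipilimumab meets the discontinuation criteria, nivolumab with BMS-986207 or placebo may go on.
- Section 7.4.3 is headed "Management Algorithms for Nivolumab plus Ipilimumab ± BMS-986207" and refers sites to Appendix 6 for groups of adverse events that include the gastrointestinal group.
- Appendix 6 describes its own status: "These general guidelines constitute guidance to the Investigator".

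**The concern.** A site managing Grade 3 colitis is sent by Section 7.4.3 to the GI algorithm. There it finds an explicit restart threshold for nivolumab plus ipilimumab, which is the active treatment in Arm B and the backbone in Arm A. That threshold is not the one in Table 7.4.2-1. The footnote's referral back to the protocol covers other combinations only, and it speaks of delay and discontinuation rather than resumption. Nowhere do the documents say that the table overrides the appendix, so a reader has to work out precedence from several sections.

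The drugs that restart are also described differently. Appendix 6 speaks of nivolumab monotherapy. The table row names nivolumab with BMS-986207 and omits the placebo. Section 7.4.2 has BMS-986207 or its placebo restart together with nivolumab.

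What is at stake is re-exposure after a serious toxicity. Section 3.3.1 lists diarrhea among the characteristic immune-related toxicities of nivolumab plus ipilimumab, and Table 3.3.1-1 names the Appendix 6 algorithms as the mitigation for immune-mediated events. A site that follows the footnote could restart treatment at a point where Section 7.4.2 does not yet allow it.

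**Working it through.** No sample size, event count or probability is involved, so the check is a comparison of texts.

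**Step 1. Do the two thresholds differ?** The event (diarrhea or colitis) and the grade (3) are the same, and ipilimumab is stopped in both. For a participant whose Grade 3 event is improving, taking a baseline of Grade 0 or Grade 1:

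| Baseline | Grade when redosing is considered | Appendix 6 footnote | Table 7.4.2-1 |
|---|---|---|---|
| 0 | 0 | may resume | may resume |
| 0 | 1 | may resume | may not resume |
| 1 | 1 | may resume | may resume |
| 0 or 1 | 2 or higher | may not resume | may not resume |

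The rules disagree in one row only: baseline below Grade 1, with symptoms at Grade 1 and not yet back to baseline. A participant who recovers fully meets both rules, and so does one who started at Grade 1 and has returned to it.

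**Step 2. Does the protocol body fix the rule for both arms?** Yes. Section 7.4.1 applies the table to nivolumab, ipilimumab and the blinded product, and sets the criteria for BMS-986207 or placebo equal to those for nivolumab because of the blind. Section 7.4.2 then requires that the table's conditions be met before treatment restarts. Neither step needs the treatment assignment.

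**Step 3. Does the appendix yield to the table on its own terms?** Not expressly. The closing sentence of the footnote refers other combinations to the protocol. It does not refer nivolumab plus ipilimumab there, and it does not mention resumption. The hepatic page of the same appendix carries a footnote that points to the protocol's delay and discontinuation criteria without limiting this to other combinations. The GI flowchart itself is not in the text reviewed, so any wording inside it could not be checked.

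**Step 4. Which drugs restart?** Sections 7.4.2 and 8.1.1 together give one answer for both arms: nivolumab with BMS-986207 or its placebo. The footnote (nivolumab alone) and the table row (no mention of placebo) are each worded differently from that answer.

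**The case against.** The strongest reply is that the protocol already settles the matter. Resumption has its own section, 7.4.2, which makes Table 7.4.2-1 a condition, and Section 7.4.1 extends the table to every study drug. Appendix 6 calls itself general guidance and says it covers all immuno-oncology agents and regimens. Its pages are dated 28-Sep-2020, before the original protocol of 30-Mar-2021, and the same footnote covers a nivolumab monotherapy regimen that is not an arm of this trial. Section 7.4.3 invokes the appendix as guidance on assessing and managing events, not as the rule for restarting. A careful site would therefore follow the table.

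Most of this stands, and it rules out a stronger reading. From the footnote alone, a reader might infer that Arm B falls under nivolumab plus ipilimumab and Arm A under other combinations, so that a blinded site cannot tell which rule applies. Sections 7.4.1 and 7.4.2 do not support that, because they set one rule for both arms. Nor does the drug list need to be created, since Sections 7.4.2 and 8.1.1 already supply it.

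The reply does not remove the conflict in wording. Section 7.4.3 brings the appendix into this trial under a heading that names the regimen: "Nivolumab, ipilimumab, and BMS-986207 are considered IO agents and the management algorithms in" Appendix 6 are offered for these agents. The footnote states a threshold for nivolumab plus ipilimumab outright, and precedence has to be inferred.

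**Conclusion.** The point holds as a narrow internal inconsistency of low severity. A general guidance appendix and the trial-specific table give different recovery thresholds for the same event and grade. The operative rule can be worked out from Sections 7.4.1 and 7.4.2, but it is not stated as prevailing over Appendix 6.

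Its size is the single disagreeing row of the comparison, which is less than every Grade 3 case with a Grade 0 baseline. The documents give no rate for Grade 3 diarrhea or colitis or for recovery that stalls at Grade 1, so no number of participants can be attached. A reader might also infer that recurrence counts or efficacy results would vary with site practice; the documents show no such effect, and none is claimed here.

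The conclusion assumes that baseline is Grade 0 or 1 and that the unseen GI flowchart contains no precedence statement. If it does contain one, the point shrinks to tidying the footnote. No view is taken on which threshold is clinically right.

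**What to change.** Either of two edits is enough.

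1. Reconcile the Appendix 6 GI footnote with the Grade 3 row of Table 7.4.2-1, so that both give one recovery threshold and name the same resuming drugs, including the placebo.
2. Add a sentence, in Section 7.4.3 or at the head of Appendix 6, saying which passage governs resumption where they differ.

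The clinical team decides the threshold. The cost is one footnote, one table cell or one sentence. Design, sample size and analysis are unaffected.
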